5. STUDY POPULATION

5.1. General

The ITT analysis set (see Section 3.2) will be used for all study population summaries unless otherwise specified. Summaries will be presented by treatment groups and overall. Treatment groups are

• Fremanezumab at 225 mg sc monthly (approximately every 4 weeks) through week 36

Note: for patients in 900 mg iv loading dose group from both Study TV48125-CNS-30056 and TV48125-CNS-30057 and patients in 675-mg sc loading dose group from Study TV48125-CNS-30057

• Fremanezumab at 675 mg sc quarterly (approximately every 12 weeks) through week 36

Note: for patients in 675 mg sc and placebo group from Study TV48125-CNS-30056

• Fremanezumab 675-mg sc loading dose followed by monthly (approximately every 4 weeks) fremanezumab at 225 mg sc through week 36

Note: for patients in placebo group from Study TV48125-CNS-30057

In addition, summaries will be presented by indication (Episodic CH [patients from TV48125-CNS-30056] and Chronic CH [patients from TV48125-CNS-30057]) and the treatment groups.

5.2. Patient Disposition

Data from patients screened; patients screened but not enrolled and reason for not enrolled; patients who are enrolled; patients enrolled for ADA only; patients in ITT analysis set (enrolled for treatment), patients in ITT analysis set but not treated; patients in the safety and other analysis sets; patients who complete the treatment; patients who did not complete the treatment and reason; patients who complete the study; patients who withdraw from the study early and the reason will be summarized using descriptive statistics.

The summary will be presented for all patients.

5.3. Demographics and Baseline Characteristics

Patient's demographics and baseline characteristics data including age, age group (<40 years or ≥40 years), gender, race, race group (white or other), ethnicity, region (US/Canada or other), baseline weight (kg), baseline height (cm), baseline body mass index (kg/m²), and preventive medication use (yes or no) at screening will be summarized using descriptive statistics for all analysis sets.

Baseline weight, baseline height, and baseline body mass index are the same baseline values in the pivotal studies, the last observed data before the administration of the first dose of the IMP in the pivotal study.

Data for ADA only patients will also be presented separately.

5.4. Medical History

Medical history refers to data collected in the pivotal studies.

All medical history abnormalities will be coded using the Medical Dictionary for Regulatory Activities (MedDRA). The incidence of medical history abnormalities will be summarized using descriptive statistics by system organ class (SOC) and preferred term. Patients are counted only once in each SOC and only once in each preferred term.

Data for ADA only patients will also be presented separately.

5.5. Prior Therapy and Medication

Prior medications will include all medications taken prior to the administration of the first dose of the IMP in the pivotal studies.

All prior medications or therapy will be coded using the World Health Organization Drug Dictionary of medical codes (WHO Drug). The incidence of prior medications or therapy will be summarized by therapeutic class and preferred term using descriptive statistics. Patients are counted only once in each therapeutic class category, and only once in each preferred term category.

The prior medications will be summarized by the following indications categories:

- preventive medication from Appendix H of the study protocol for CH
- preventive medication from Appendix H of the study protocol for other reason than CH
- butalbital for CH
- butalbital for other reason than CH
- triptans for CH
- triptans for other reason than CH
- ergots for CH
- ergots for other reason than CH
- non-steroidal anti-inflammatory drugs (NSAIDs) for CH
- NSAIDs for other reason than CH
- opioids for CH
- opioids for other reason than CH
- other

Data for ADA only patients will also be presented separately.

5.6. Childbearing Potential and Methods of Contraception

[figure not shown]
Information related to reproductive system findings will be collected at visit 1. Data will be listed.

[figure not shown]
5.7. Physical Examinations

[figure not shown]
Patients with at least 1 abnormal finding (overall) and abnormal findings for each category will be summarized.

[figure not shown]
5.8. Study Protocol Deviations

[figure not shown]
Data from patients with any important protocol deviations during the study will be summarized overall and for each category using descriptive statistics.

7. MULTIPLE COMPARISONS AND MULTIPLICITY

No inferential analysis will be performed in this study.

8. SAFETY ANALYSIS

8.1. General

The safety analysis set will be used for all safety analyses unless otherwise specified. Summaries will be presented by treatment groups as actually received and overall. In addition, summaries will be presented by indication (Episodic CH [patients from TV48125-CNS-30056] and Chronic CH [patients from TV48125-CNS-30057]) and the treatment groups.

8.2. Duration of Exposure to Study Drug

Study IMP will be administrated visit 1 through visit 10 with three treatment groups as follows:

• Fremanezumab at 225 mg sc monthly (approximately every 4 weeks) through week 36

Note: for patients in 900 mg iv loading dose group from Study TV48125-CNS-30056 or TV48125-CNS-30057 and patients in 675-mg sc loading dose group from Study TV48125-CNS-30057

• Fremanezumab at 675 mg sc quarterly (approximately every 12 weeks) through week 36

Note: for patients in 675 mg sc and placebo group from Study TV48125-CNS-30056

• Fremanezumab 675-mg sc loading dose followed by monthly (approximately every 4 weeks) fremanezumab at 225 mg sc through week 36

Note: for patients in placebo group from Study TV48125-CNS-30057

There are total 10 dosing visits (see Figure 1). Patients will receive either injection(s) of test IMP or injection(s) of placebo IMP at each visit.

Duration of treatment (days) and number of doses (≥ 1 dose, ≥ 2 doses, ≥ 3 doses, . . ., 10 dose) will be summarized using descriptive statistics.

IMP administration and accountability data will be listed.

8.4. Injection Site Assessments

Injection site assessments will be performed immediately (+10 minute) and 1 hour (±15 minutes) after receiving each dose of the IMP visits 1 through 10. The injection sites will be assessed for erythema, induration, and ecchymosis. More details are in Section 7.11 of the study protocol.

Injection-site reactions should be recorded as adverse events. Injection-site related adverse events will be summarized as indicated in Section 8.3.

8.5. Hypersensitivity/Anaphylaxis

Patients will be assessed for suspected anaphylaxis reaction during and after administration of the IMP (through 1 hour postdose) at visits 1 through 10. Data will be summarized using descriptive statistics.

The number of patients with suspected anaphylaxis reactions and number of suspected anaphylaxis reactions per patient will be summarized using descriptive statistics.

The relative time of suspected event will be calculated as date/time of suspected event - date/time of most current IMP administration and summarized using descriptive statistics. If a patient has more than one suspected anaphylaxis reactions, the earliest time will be used for the calculation.

Data will be listed.

8.6. Electronic Columbia Suicide Severity Rating Scale

The eC-SSRS Since Last Visit version will be completed by the patient at visits 2 through 12, including unscheduled visits. Any positive findings on the eC-SSRS 'Since Last Visit' version requires evaluation by a physician or doctoral-level psychologist.

Data for patients with positive findings (having suicidal ideation or suicidal behavior) will be listed.

8.7. Deaths

If any patient dies during the study, all relevant information will be discussed in the patient narrative included in the clinical study report.

8.8. Clinical Laboratory Tests

Clinical laboratory tests (serum chemistry, hematology, coagulation, and urinalysis; see protocol Appendix M) will be performed at visits 4, 7, 10 and 11 using the central laboratory. All clinical laboratory test results outside of the reference range will be judged by the investigator as belonging to one of the following categories:

- abnormal and not clinically significant
- abnormal and clinically significant

A laboratory test result that is judged by the investigator as clinically significant will be recorded on the source documentation and the CRF as an adverse event, and monitored as described in Section 7.1.2 of the protocol.

Laboratory test results will be presented in standard international (SI) units in summaries. Laboratory values and changes from baseline to each visit and Last Assessment will be summarized using descriptive statistics. Shifts (below [low], within [normal], and above [high] the normal range) from baseline to each postbaseline visit and the Last Assessment will be summarized using patient counts. Baseline is defined as the last observed data before the administration of the first dose of the IMP in the pivotal study.

The potentially clinically significant abnormal values will be derived using criteria specified in Table 4 based on all postbaseline values (including scheduled, unscheduled, and withdrawal visits). The overall incidence of potentially clinically significant abnormal values will be summarized for laboratory variables using descriptive statistics by treatment group. Listings for patients who have potentially clinically significant abnormal laboratory data will be presented.

Table 4: Criteria for Potentially Clinically Significant Laboratory Values

Test		Criterion value
Serum chemistry		
ALT		≥3x ULN
AST		≥3x ULN
ALP		≥3x ULN
GGT		≥3x ULN
LDH		≥3x ULN
BUN		≥10.71 mmol/L
Creatinine		≥177 µmol/L
Bilirubin (total)		≥34.2 µmol/L
Hematology		
Hematocrit	Men	<0.37 L/L
	Women	<0.32 L/L
Hemoglobin	Men	≤115 g/L
	Women	≤95 g/L
WBC counts		≤3 x 10 ⁹ /L
		≥20 x 10 ⁹ /L
Eosinophils		≥10%
ANC		$\leq 1 \times 10^9/L$
Platelet counts		≤75 x 10 ⁹ /L
		≥700 x 10 ⁹ /L
Urinalysis		
HGB		≥2 unit increase from baseline
Glucose		≥2 unit increase from baseline
Ketones		≥2 unit increase from baseline
Total protein		≥2 unit increase from baseline

ALP=alkaline phosphatase; ALT=alanine aminotransferase; ANC=absolute neutrophil count AST=aspartate aminotransferase; BUN=blood urea nitrogen; GGT=gamma- glutamyl transpeptidase; HGB=hemoglobin; LDH=lactate dehydrogenase; RBC=red blood cell; ULN=upper limit of normal range; WBC=white blood cell

Serum beta-human chorionic gonadotropin (β -HCG) tests will be performed for all women of childbearing potential at visit 11. Urine β -HCG tests will be performed for women of childbearing potential at visits 1 through 10. Positive pregnancy test results will be listed.

Currently menstruating (yes, no, n/a) information will be collected from each female patient prior to blood and urine collection for clinical laboratory tests. Data will be listed.

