1. STUDY ENDPOINTS

1.1. Primary Objective and Endpoints

The primary objective of this study is to evaluate the long-term safety of fremanezumab in adult patients with cluster headache (CH).

Safety endpoints are as follows:

- occurrence of adverse events throughout the study
- changes from baseline (day 0 of the Phase 3 pivotal efficacy studies) in clinical laboratory (serum chemistry, hematology, coagulation, and urinalysis) test results
- changes from baseline (day 0 of the Phase 3 pivotal efficacy studies) in vital signs (pulse, systolic and diastolic blood pressure, and oral temperature) measurements

 Note: Oxygen saturation will be measured in cases of suspected anaphylaxis and severe hypersensitivity. Respiratory rate will also be measured in these cases but not as a standard vital sign.
- abnormal standard 12-lead electrocardiogram (ECG) findings
- clinically significant changes in physical examination, including body weight
- occurrence of injection site reactions (ie, erythema, induration, and ecchymosis) and/or injection site pain
- occurrence of anaphylaxis and hypersensitivity reactions
- use of concomitant medications during the study
- suicidal ideation and behavior as measured by the electronic Columbia Suicide Severity Rating Scale (eC-SSRS)

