3.3. Safety Analysis Set

4. GENERAL ISSUES FOR DATA ANALYSIS

4.1. General

Descriptive statistics for continuous variables include count (n), mean, standard deviation (SD), standard error (SE), median, minimum, and maximum. In addition, for fremanezumab concentration percentage coefficient of variation (%CV) and geometric mean will also be calculated. Descriptive statistics for categorical variables include patient counts and percentages, and a missing category will be displayed as appropriate.

Summaries of potentially clinically significant abnormal values for clinical laboratory tests and vital signs values will include all postbaseline values (including scheduled, unscheduled, and early withdrawal visits).

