8.10. Vital Signs

Vital signs (pulse, systolic and diastolic blood pressure, and body temperature) will be measured at each (visit 2 through 12). Weight will be measured at visits 2, 4, 5, 7, 8, 10, 11, and 12. Any vital sign value that is judged by the investigator as a clinically significant change (worsening) from a baseline value will be considered an adverse event, recorded on the source documentation and transcribed onto the CRF, and monitored as described in Section 7.1.2 of the protocol.

Vital signs (including weight) values and changes from baseline to each visit and the Last Assessment will be summarized using descriptive statistics. The incidence of potentially clinically significant abnormal values will be summarized for selected vital signs using descriptive statistics. Baseline is defined as the last observed data before the administration of the first dose of the IMP in the pivotal study.

Table 5 specifies the criteria for identifying vital signs as potentially clinically significant abnormal values. Note that in order to qualify as potentially clinically significant abnormal, a value needs to meet both criteria below: ie, have a value beyond the criterion value and a change of at least the magnitude specified in the change relative to baseline column. The potentially clinically significant abnormal vital signs values will include all postbaseline values (including scheduled, unscheduled, and early withdrawal visits) for the summaries.

Table 5: Criteria for Potentially Clinically Significant Vital Signs

Vital Sign	Criterion value	Change relative to baseline
Pulse	≥120 bpm	Increase of ≥15 bpm
	≤50 bpm	Decrease of ≥15 bpm
Systolic blood pressure	≥180 mm Hg	Increase of ≥20 mm Hg
	≤90 mm Hg	Decrease of ≥20 mm Hg
Diastolic blood pressure	≥105 mm Hg	Increase of ≥15 mm Hg
	≤50 mm Hg	Decrease of ≥15 mm Hg
Temperature	≥38.3°C	Change of ≥1.1°C

bpm=beats per minute

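### For chemistry and hematology, the SAP's incidence of potentially clinically significant laboratory values has no baseline condition, so abnormality that was already present can be reported as incidence

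*SAP*

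**What the plan says.** SAP 8.8 states that "potentially clinically significant abnormal values will be derived using criteria specified in Table 4 based on all postbaseline values", with scheduled, unscheduled and withdrawal visits all included; SAP 4.1 repeats the all-postbaseline rule. SAP 8.8 then defines the output: "The overall incidence of potentially clinically significant abnormal values will be summarized for laboratory variables using descriptive statistics by treatment group". Patients with such values are also listed.

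Table 4 sets two kinds of criterion. The serum chemistry and hematology rows give an absolute limit or a multiple of the upper limit of normal (ULN), with no reference to the patient's earlier value. The four urinalysis rows instead require a "≥2 unit increase from baseline".

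For vital signs, SAP 8.10 states that "a value needs to meet both criteria below: ie, have a value beyond the criterion value and a change of at least the magnitude" given in the change column of Table 5.

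On the reference point, SAP 8.8 says: "Baseline is defined as the last observed data before the administration of the first dose of the IMP in the pivotal study". SAP 1.1 lists "changes from baseline (day 0 of the Phase 3 pivotal efficacy studies) in clinical laboratory" results among the safety endpoints. SAP 8.8 also provides change-from-baseline summaries and shift tables by low, normal and high relative to the normal range.

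**The concern.** A reader takes an incidence in a long-term safety report to mean something that arose after treatment began. For chemistry and hematology the planned figure mixes two groups: patients who crossed the limit after baseline, and patients who were past it before any study drug and stayed there. A patient with eosinophils at 10% or more before the first pivotal dose and at a later visit is counted exactly like one who went from normal to 10%.

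In a placebo-controlled study the control column would show roughly how much of this is background. Here Protocol 3.3 gives every treated patient fremanezumab, and placebo injections serve only the blind. The patient's own baseline is the only reference available. The SAP also breaks safety summaries down by treatment group and indication (SAP 8.1), so a few long-standing abnormalities can visibly move a small cell.

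**Working it through.** The plan states no expected rate, so there is no figure to reproduce. The check is a count of the criteria followed by an illustration.

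**Criteria by type, SAP Tables 4 and 5**

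| Group | Tests | Rows | Change from baseline required? |
|---|---|---|---|
| Serum chemistry | 8 | 8 | No |
| Hematology | 6 | 10 | No |
| Urinalysis | 4 | 4 | Yes |
| Vital signs (Table 5) | 4 | 7 | Yes, plus an absolute limit |

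In Table 4, 8 + 6 = 14 of 18 tests (18 of 22 rows) have no baseline condition.

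**Which of the 14 are exposed.** Protocol 4.2 keeps patients out of the treatment portion if ALT or AST is confirmed above 1.5 x ULN, or if creatinine is above 1.5 x ULN. The other 11 tests have no numeric entry limit: ALP, GGT, LDH, BUN, bilirubin, hematocrit, hemoglobin, white cells, eosinophils, neutrophils and platelets. They fall only under investigator judgment (exclusion c, inclusion g).

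**Illustration for one test.** Let b be the share past the limit at baseline, s the chance that such a patient has at least one postbaseline value past it, and i the true new-onset rate in everyone else. None of the three is in the documents; all are assumed.

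Reported rate = b x s + (1 - b) x i. With s = 0.8 and i = 1%:

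- b = 0: 1.00%
- b = 1%: 0.01 x 0.8 + 0.99 x 0.01 = 1.79%
- b = 3%: 0.03 x 0.8 + 0.97 x 0.01 = 3.37%
- b = 5%: 0.05 x 0.8 + 0.95 x 0.01 = 4.95%

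The excess over i is b x (s - i), for example 0.05 x 0.79 = 3.95 percentage points.

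**Sensitivity to persistence.** Laboratory tests are scheduled at four visits (4, 7, 10 and 11). If a patient past the limit at baseline is past it at each visit with probability q, independently, then s = 1 - (1 - q)^4. This is 93.75% for q = 0.5 and 99.84% for q = 0.8. With i = 1% the reported rate is then 1.93% to 1.99% at b = 1% and 5.64% to 5.94% at b = 5%. The value s = 0.8 is therefore not an extreme choice.

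**What a split would show.** Take the planned 360 treated patients, b = 5%, s = 0.8 and i = 1%. At baseline 18 are past the limit, of whom 14.4 are flagged again. The other 342 yield 3.4 new cases. The planned table shows 17.8/360 = 4.95%; the split shows 3.4/342 = 1.0% beside 14.4/18.

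**The case against.** The strongest reply is that this table is a supplementary screen. Changes from baseline and normal-range shifts already serve the endpoint in SAP 1.1, and Protocol 9.7 asks for boundaries that identify notable changes or values, so flagging absolute values is within the protocol. That stands: a reader might infer that the SAP breaches the protocol or leaves the endpoint unanalysed, and it does neither.

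Baseline status is also not lost. For the tests with ULN-multiple limits, anyone past the limit at baseline must sit in the high row of the shift table, which gives an upper bound on b, and the flagged patients are listed. Clinically significant results become adverse events, which Protocol 7.1.1 restricts to conditions that develop or worsen. These help only in part. GGT steady at 3.2 x ULN and GGT rising from 1.2 to 3.5 x ULN both read high-to-high, and neither listing nor adverse-event table corrects the incidence figure.

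A reader might further infer that all laboratory tests, or every column, are inflated. The documents do not support that. Urinalysis is protected by its own criterion. The ALT, AST and creatinine limits apply at entry to this study, after the pivotal baseline, so they largely block a persisting elevation. They may not do so fully: Protocol Appendix J refers to patients with baseline ALT or AST of 2 to 3 x ULN who may be enrolled, which needs reconciling with Protocol 4.2.

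Finally, simply dropping patients past the limit at baseline would hide real worsening, such as GGT going from 3 to 10 x ULN. Nor is that the vital-signs rule: under Table 5 a pulse going from 122 to 140 still counts. This objection stands and shapes the remedy.

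**Conclusion.** The point holds for the 14 chemistry and hematology tests and is minor. The planned incidence can include persistent abnormality that predates any study drug, with no untreated arm to reveal it. The tests mainly affected are GGT, ALP, LDH, BUN, bilirubin and the hematology tests.

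The size cannot be derived from the documents. It is nil if almost nobody was past the limit at baseline, which is plausible for several tests. The range of about 1.8% to 5.0% for a true 1% rests on assumed values of b (1% to 5%), s (80%) and i (1%). It shows how the rule behaves and should not be read as an estimate of bias in this trial. The pivotal-study eligibility rules, which partly determine b, are not in these documents.

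**What to change.** In SAP 8.8, keep the planned all-postbaseline count and the listing. For each chemistry and hematology test, split the table by whether the patient met the Table 4 criterion at the pivotal baseline:

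- patients not meeting it at baseline: the number who met it afterwards, over that denominator, labelled as treatment-emergent;
- patients meeting it at baseline: their number, and how many met it again afterwards, so that worsening from an abnormal baseline stays visible and can be followed up in the listing.

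Urinalysis needs no change. Because the reference is the pivotal baseline, an abnormality that arose on fremanezumab during the pivotal study and persists still counts as new.

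The data are already collected. The cost is one extra table split and a slightly different N per test.

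### Urinary haemoglobin PCS incidence mixes menstrual contamination with other causes, because the recorded menstruation status is only listed (minor)

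*SAP*

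**What the plan says.** SAP 8.8 sets the rule: "The potentially clinically significant abnormal values will be derived using criteria specified in Table 4 based on all postbaseline values". The pool of values is unrestricted: "based on all postbaseline values (including scheduled, unscheduled, and withdrawal visits"). For urinary haemoglobin (HGB), the Urinalysis block of SAP Table 4 gives the criterion as "≥2 unit increase from baseline", with no qualifier for sex or menstruation. Blood haematocrit and haemoglobin in the same table do have separate limits for men and women.

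The reference value comes from the parent trial: "Baseline is defined as the last observed data before the administration of the first dose of the IMP in the pivotal study". Laboratory tests "will be performed at visits 4, 7, 10 and 11 using the central laboratory", that is, at weeks 12, 24, 36 and 40. The output is a table: "The overall incidence of potentially clinically significant abnormal values will be summarized for laboratory variables using descriptive statistics by treatment group". Patients with PCS laboratory values are also listed.

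On menstruation, SAP 8.8 states: "Currently menstruating (yes, no, n/a) information will be collected from each female patient prior to blood and urine collection for clinical laboratory tests". The instruction that follows is "Data will be listed". Protocol Table 4, footnote m, requires the same collection and attaches no analysis rule. SAP section 17 records no change to the protocol analyses.

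**The concern.** Menstrual blood in a urine sample can raise the haemoglobin reading without any urinary tract bleeding. The plan asks about menstruation immediately before the sample is taken, which suggests that the answer is meant to help interpret the result. The derivation then ignores it, so a contaminated sample that reaches the threshold counts the same as one with true haematuria.

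Change in laboratory results, urinalysis included, is one of the primary safety endpoints (SAP 1.1). Every treated patient receives fremanezumab (Protocol 3.3), so no concurrent placebo rate shows how many flags would occur without the drug. The SAP's treatment groups also pool patients from two pivotal studies and several original arms (SAP 5.1). If the share of menstruating women differs between groups, the haemoglobin row could show a difference between regimens that has nothing to do with dose.

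**Working it through.** The plan gives no expected PCS rate, share of women or menstruation rate, so there is no figure to reproduce. The check is a reading of the rule, followed by an illustration.

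**Does anything keep contaminated samples out of the count?**

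- *Threshold.* A rise of 2 or more units is required. This removes small rises, whatever their cause.
- *Values used.* All postbaseline values enter, with no exclusion for menstruation.
- *Investigator judgement.* Under SAP 8.8 it decides which out-of-range results become adverse events. The PCS flag comes from Table 4 alone.
- *Listings.* The PCS listing and the menstruation listing allow each case to be checked, but the tabulated count stays the same.
- *Eligibility.* Inclusion criterion d in Protocol 4.1, read literally, would admit only sterile or postmenopausal women. Criterion e and the pregnancy tests at visits 1 to 11 show that women of childbearing potential do enrol.

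Nothing in either document removes a menstrual rise of 2 or more units from the incidence.

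**How often could a sample be exposed?** The cycle inputs below are assumptions, not document figures, and apply to a woman who menstruates throughout the study. Let f be the share of days with bleeding. If cycle phase is independent at each visit, the chance of a non-menstrual baseline and at least one of the four scheduled samples during menses is

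(1 − f) × [1 − (1 − f)^4]

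| Bleeding days in 28 | f | At least 1 of 4 | With clean baseline |
|---|---|---|---|
| 3 | 0.107 | 0.364 | 0.325 |
| 5 | 0.179 | 0.545 | 0.447 |
| 7 | 0.250 | 0.684 | 0.513 |

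Independence is doubtful, because the visits fall at multiples of 4 weeks. A simulation with the planned spacing and ±3-day windows, for 3 to 7 bleeding days, gives:

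| Cycle | Clean baseline and at least 1 exposed sample |
|---|---|
| Exactly 28 days | about 0.15 |
| 28 days, SD 2 | 0.24 to 0.30 |
| 30 days, SD 3 | 0.30 to 0.47 |

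**From exposure to a PCS flag.** If a share q of contaminated samples rises by 2 or more units, the independent-timing formula becomes (1 − f) × [1 − (1 − fq)^4]:

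- 4 days, q = 0.25: 0.857 × (1 − 0.964^4) = 0.116
- 5 days, q = 0.5: 0.821 × (1 − 0.911^4) = 0.256
- 6 days, q = 1: 0.786 × (1 − 0.786^4) = 0.486

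With exact 28-day cycles and the visit windows, q from 0.25 to 1 gives about 5% to 15%. No document supplies q, so these figures show only how strongly the answer depends on it.

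**Direction.** A woman who is menstruating at baseline has a raised reference value, so a later true rise can be missed. There is one baseline sample and up to four scheduled postbaseline samples, so upward bias is the likelier direction, but both are possible.

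**The case against.** The strongest case on the other side is that this is one descriptive row and is partly handled already. The values are only potentially significant, the investigator judges clinical significance separately, no inferential analysis is planned (SAP section 7), and the two listings let a reader check each flagged woman. Counting every value is also the cautious choice for safety. All of this stands and limits the importance of the point. It does not change the tabulated incidence, which is what a reader of the report will see first.

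A second objection is that the illustration overstates exposure. Women with potentially fertile partners must use highly effective contraception, and hormonal methods qualify (Protocol Appendix E), so natural cycling cannot be assumed. Patients with chronic cluster headache were asked to stop treatment from 15 June 2018, and SAP 2.1 says the study finished early, in Q2/2019, so some women will have fewer than four samples. This stands too.

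A third objection concerns the remedy. Dropping menstruating samples from the only count could discard true haematuria and would leave a menstrual baseline uncorrected. That is right, and is why the all-samples count should remain the main one.

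A reader might also infer more than the documents support:

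- *Every menstruating woman with a clean baseline becomes a PCS case.* She counts only if the rise reaches 2 units.
- *The flags are attributed to the drug.* Relatedness is judged on adverse events (Protocol 7.1.4), not on PCS values.
- *The urine protein row is biased in the same way.* Neither document supports this.
- *Exact 28-day cycles bring exposure close to zero.* The ±3-day windows leave it at about 0.15.

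**Conclusion.** The point holds as a gap in the derivation rule. Rises of 2 or more units in urinary haemoglobin caused by menstrual contamination enter the PCS incidence by treatment group, although the fact needed to separate them is collected before the same clinical laboratory urine sample. The statement covers that sampling only; the plan does not say the question is asked before urine pregnancy tests or biomarker urine.

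The effect on the reported incidence is unknown. The exposure chances apply per menstruating woman, rest on assumed bleeding days and cycle regularity, and are not PCS rates. The documents do not say how many of the roughly 360 patients planned for treatment menstruate, so no count of affected patients can be given. The importance is minor: one descriptive row, bias possible in both directions, and listings that allow case review.

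**What to change.** In SAP 8.8:

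1. Keep the PCS incidence for urinary haemoglobin from all postbaseline samples as the main count, as planned.
2. Add a second count for the same criterion that excludes samples with menstruation status recorded as yes. Its denominator is patients with at least one remaining postbaseline sample.
3. Mark samples taken during menstruation in the PCS listing.
4. Mark the baseline sample in the same way if the pivotal studies recorded the status; these documents do not show whether they did.

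The cost is a sentence or two in the SAP, one extra table row and a merge of two datasets that are already planned. The second count has slightly fewer evaluable urine samples in women. No visit or procedure changes, and because the all-samples count stays, no case is hidden.
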